7.0 Informed Consent

Each subject shall review, understand, and sign an informed consent form (ICF) that has been approved by the investigational site’s Institutional Review Board (IRB) for use in this study. The consenting process must be done in accordance to the policies and procedures of that specific investigational site, and as specified in this protocol.

The original signed informed consent form shall be retained in the subject’s study files. A copy of the informed consent form shall be provided to the subject.

Any amendments made to this protocol that result in a change in the informed consent must be submitted to the IRBs. It is left to the discretion of each IRB whether previously enrolled subjects must sign the new version of the consent form at the next study encounter, according to the IRB policies in place at that institution.

8.0 Site Responsibilities, Reporting and Recordkeeping

The Principal Investigator has the following responsibilities:

- Submit the Clinical Investigation Plan/Protocol and the informed consent form to the Investigation Site IRB/EC for approval. A formal, written approval to participate in the study from the IRB/EC shall be provided to the Sponsor prior to any patient enrollment.
- Protect the rights, safety and welfare of subjects;
- Conduct the study in accordance with the signed investigator agreement with the Sponsor, the Clinical Investigation Plan/Protocol, the IDE regulations and any other requirements imposed by the FDA and IRB/EC;
- While waiting for approval of the IDE application, the Principal Investigator may determine whether or not potential subjects would be interested in participating in the study, but cannot request written informed consent or allow any subjects to participate before obtaining IRB/EC and FDA approval;
- Obtain informed consent per the IDE requirements of 21 CFR Part 50 (Protection of Human Subjects) and the standard of care at the Investigation Site;
- Ensure that the investigational device is only used for subjects under his/her supervision in this study and shall not supply the investigational devices to any person not authorized to receive it;
- Complete the CRF forms, (copies of the Case Report Forms are provided by MicroVention) for each Subject enrolled in the study per the requirements of the Clinical Investigation Plan/Protocol and the Manual of Operating Procedures;
- Upon completion or termination of the study or the investigator's participation in the study, or at the request of the Sponsor, the Principal Investigator shall return to the Sponsor any remaining supply of the investigational devices, or dispose of them as the Sponsor directs;
- The Principal Investigator shall disclose to the Sponsor sufficient accurate financial information to allow the Sponsor to submit certification or disclosure of financial interests under 21 CFR Part 54 (Financial Disclosure by Clinical Investigators). The Principal Investigator shall update the information if any relevant changes occur during the course of the study and for one year following completion of the study.

The Principal Investigator shall provide the following reports in a timely manner:

- A written report shall be submitted to the Investigation Site IRB/EC and Sponsor of any Unanticipated Adverse Device Effect as soon as possible (i.e. within 24 hours) but no later than 10 working days after the investigator first learns of the effect;
- A written report shall be submitted to the Sponsor regarding a withdrawal of study approval from the IRB/EC within 5 working days;
- A progress report shall be submitted to the Sponsor, Monitor and IRB/EC at regular intervals but no less than on a yearly basis. The report to the IRB/EC shall include a request for approval to continue the study. The status of the study shall be shared with the IRB/EC and Sponsor upon request.

- If a FRED System is used without obtaining informed consent, a report shall be provided to the IRB/EC and Sponsor within 5 working days after the use occurs.
- The Sponsor shall be notified of any deviation from the Clinical Investigation Plan/Protocol to protect the life or physical well-being of a Subject in an emergency. The notice shall be provided as soon as possible (i.e. 24 hours) but no later than 5 working days after the emergency occurred. If it is not an emergency, prior approval from the Sponsor shall be required for changes in or deviations from the protocol.
- Any proposed amendments to the protocol or informed consent form that have IRB/EC approval shall be submitted in written form to the Sponsor.
- The IRB /EC shall be notified of any changes to the status of the study including completion, termination or other necessary changes, according to the IRB policies in place at that institution.
- A letter of notification of the completion, termination or discontinuation of the study shall be submitted to the IRB/EC.
- A final report shall be submitted to the IRB/EC and Sponsor within 3 months after termination or completion of the study.

The Principal Investigator shall maintain accurate and complete records relating to the study. These records shall include:

- The Clinical Investigation Plan/Protocol and any documentation (date and reason) for each deviation from the protocol
- All correspondence including required reports
- Records of receipt, use and disposition of the investigational device
- Records of each Subject's case history and exposure to the investigational device

A detailed description of the responsibilities of the investigational sites is found in the study Manual of Operating Procedures. The site Principal Investigator is responsible for site adherence to these expectations.

9.0 Sponsor Led Device Training

The FRED® device is intended to be used by interventional neuro-radiologists or neurosurgeons who are trained in endovascular procedures and who have experience with embolization of intracranial aneurysms.

All investigators and co-investigators will undergo standardized training prior to study participation. As part of the training program, MicroVention personnel or designee will provide hands-on training in the use of the device using a bench top model (or equivalent) to familiarize the investigator with the use of the FRED System. In addition, the investigators will attend didactic sessions to cover the directions for use, preparation of the FRED System and procedure planning.

In addition to didactic sessions and hands-on training, the study personnel at each study site will undergo protocol training and site initiation visit. Site training and initiation will be documented and the records maintained by the study sponsor.

10.0 Medications

10.1 Pre-Procedure

- Aspirin (ASA) 81-325 mg/day per oral for a minimum of 5-7 days prior to the procedure
- Clopidogrel (Plavix) 75 mg/day per oral for a minimum of 5-7 days prior to the procedure. If the Subject has an intolerance or documented contraindication to clopidogrel, another antiplatelet agent; such as P2Y12 receptor inhibitors (prasugrel or ticagrelor) may be prescribed.

If the subject has not been on dual antiplatelets (aspirin and clopidogrel) for a minimum of 5-7 days prior to the procedure, a single loading dose of aspirin 325 mg and clopidogrel 600 mg should be given at least 6 hours (but no more than 24 hours) prior to the procedure.

Platelet inhibition function tests should be performed prior to the procedure (using platelet counts or point of care assays) such as Verify Now ® (Accumetrics, US) or others. Instructions and threshold levels of platelet inhibition is provided in the Manual of Operating Procedures.

10.2 Intra-Procedure

- Heparin: A bolus of intravenous heparin should be given that is weight-adjusted to maintain the activated clotting time (ACT) near 250-300 seconds throughout the procedure. **ACT should be checked throughout the procedure at 60 minute intervals.**
- If a Glycoprotein IIb – IIIa receptor antagonist (abciximab/ReoPro®, tirofiban/Aggrastat®, or eptifibatide/Integrilin®) is used during the procedure, then ACT should be maintained at less than 220 seconds to avoid hemorrhage.

10.3 Post-Procedure

- For at least 6 months post-procedure: Aspirin (ASA) 81-325 mg/day per oral
- Clopidogrel 75 mg/day per oral or equivalent

After the initial 6 month period, 1 antiplatelet agent only should be considered and taken for lifetime. Aspirin is preferred if no contraindication.

10.4 Medication Log

Documentation of other medications that the subject takes during their participation in the study shall be collected, as described in the Manual of Operating Procedures.

11.0 Procedure

11.1 Subject Screening and Enrollment

Potential study subjects shall be assessed using the Screening Form. This includes a review of the inclusion/exclusion criteria and confirmation they are met.

For women of childbearing potential (any menses within the last 18 months unless surgically sterilized), pregnancy test (serum or urine) should be done at the time of screening.

When all items have been completed and the Screening Form has been signed by a site study physician, the subject should be given the informed consent to review and to sign. The subject shall have the opportunity to speak to a study physician regarding any questions they may have about the study. The consenting process shall be documented in the medical record according to the study site policies.

As part of standard diagnosis for neurovascular aneurysms, the subject shall be evaluated by the neurovascular team. The subject shall have an appropriate clinical evaluation (utilizing the NIHSS and mRS) performed by a qualified/certified person, a laboratory evaluation and a cerebral vascular imaging (CTA, MRA, or conventional angiography). Vascular imaging shall be evaluated for aneurysm location, aneurysm size and morphology, aneurysm neck width, and parent artery size, making sure it fulfills the angiographic inclusion criteria. The images of the aneurysm will be accessed by the Principal Investigator of the Study to confirm the patient meeting angiographic criteria.

A baseline clinical eye and ophthalmic exam must be performed by an ophthalmologist on all subjects and must be conducted within 30 days of the FRED procedure. A historical exam that was previously conducted by an ophthalmologist at most at 30 days before the procedure is acceptable. The clinical eye exam shall be performed at every visit and can be conducted by the Principal Investigator, Research Nurse, or an appropriate and delegated designee. However, an ophthalmic exam shall be performed during the screening process or if any visual deficits occur during the study, by an ophthalmologist. If any visual deficits are found at a follow-up evaluation or an adverse event of visual impairment occurs, another clinical eye and ophthalmic exam shall be conducted by an ophthalmologist and followed until the deficit has resolved.

11.2 Pre-Procedure

The pre-procedure antiplatelet medications should be prescribed as stated in section 11.1.

11.3 Intra-Procedure – FRED System Deployment

The subject shall be brought to the neurovascular angiographic suite for diagnostic cerebral angiography and endovascular aneurysm treatment with the FRED System. While the diagnostic portion of the procedure may be performed under local anesthesia and/or conscious sedation, **treatment with the FRED System must be performed under general anesthesia.**

Arterial access shall be gained using standard techniques via either a femoral, brachial or radial artery approach. A vascular sheath shall be inserted according to standard angiographic techniques. Following sheath placement, IV Heparin shall be administered to achieve an ACT between 250-300 seconds.

ACT shall be monitored at least hourly and the measurement recorded.

Initial diagnostic cerebral angiography shall be performed to accurately define the aneurysm fundus size, neck size and parent artery diameter. These measurements must be made to verify that the dimensions of the aneurysm and the size of the parent artery are compatible with the study inclusion criteria. If the measurements result in exclusion of the Subject from the study, the subject shall be withdrawn from the study and considered enrolled but not treated. The reasons for withdrawal of all Subjects shall be documented. Appropriate treatment using standard of care should proceed at the discretion of the clinician.

For complete procedure instructions, refer to the Instructions for Use (IFU) that is included in each device package.

11.4 Withdrawal Criteria

A subject can withdraw their consent to participate in the study at any time. Each site must follow their institutional policies and procedures for withdrawal of consent by a research subject.

Available data for any subject who withdraws from the study will be included in the final data analysis.

11.5 Subject withdrawal/Lost to Follow-Up

A subject can stop his/her participation in the study by withdrawing their consent. In such cases, the subject shall not be penalized for such action. Meanwhile, the subject shall be treated according to the standard practice of the institution. The reason for withdrawal shall be documented on the CRF.

Available data for subjects who withdraw from the study shall be included in the final data analysis. The same criteria shall be used for those subjects who are lost to follow-up.

11.6 Follow-Up of Subjects enrolled but not treated

A subject that is considered enrolled but not treated with the FRED System shall be closely monitored for one (1) week.

If the subject experiences a neurological event that is determined to be probably or definitely related to the FRED device by the independent Clinical Events Committee (CEC), or if the CEC is unable to determine relatedness, that subject will be followed at 30-days, 180-day and 12-months.

A subject that is considered enrolled but not treated because of a failure to continue meeting the inclusion criteria or subsequently meet the exclusion criteria, or because of a failed FRED System deployment, and who did not have an Adverse Event, will not have 30-day; 180-day and 12-month follow-up.

Prior to study enrollment, careful consideration should be given to the likelihood of a subject's ability to complete all study follow-up requirements. Names and phone numbers for additional contact persons should be recorded in the subject's study file. Attempts should be made promptly to locate a study subject after a missed visit and any barriers to ongoing participation should be discussed and remedied if possible.

Available data for any subject who has become lost to follow-up will be included in the final data analyses.

12.0 Angiographic Requirements

Qualitative Image Analysis shall be performed by a team from the imaging core lab. It is the role of the Core Laboratory to assess the angiographic outcomes including aneurysm occlusion status and parent artery patency.

12.1 Core Laboratory Angiography Assessment Methods

12.1.1 Aneurysm Occlusion

Angiographic assessment of the anatomic occlusion of the aneurysm shall be performed using the Roy and Raymond's Classification at the following time points:

[figure not shown]
- Immediately post-procedure
- 180-day follow-up
- 12-month follow-up

The angiographic assessment shall be performed by independent, blinded reviewer(s). The following occlusion characterization shall be used for reference:

Raymond Scale 1

Raymond Scale 2

Raymond Scale 3

- Complete(100%) = complete occlusion, no flow of contrast seen in the sac;
- Near Complete (>90-99%-residual neck) = partial occlusion, some flow in the neck or sac;
- Incomplete aneurysm (≤90%- residual aneurysm) = incomplete occlusion, apparent flow into the sac;

Reference: Roy D, Milot G, Raymond J. Endovascular treatment of unruptured aneurysms. *Stroke* 2001;32:1998-2004. ⁴⁷

12.1.2 Parent Artery Patency

Stenosis shall be assessed using the WASID criterion which is defined as greater than 50% luminal loss at angiographic follow up using the WASID method:

$$[1(D_{\text{stenosis}}/D_{\text{normal}})] \times 100$$

Where D_{stenosis} is the diameter of the artery at the site of the most severe stenosis and D_{normal} is the diameter of the proximal normal artery.

12.2 Site Requirements – Angiographic Imaging

Images shall be sent as DICOM electronic files uploaded onto digital media (example CD) to the Core Laboratory for analysis. The Digital Media must be labeled using the subject's FRED Study Number instead of Subject Name, for confidentiality purposes.

12.2.1 Initial Angiography

Sites shall send the following images (at a minimum):

- AP, Lateral and working projections;
- Working projections selected for FRED deployment (pre-deployment);
- Working angles (post-FRED deployment);
- If available, imaging should include 3D reconstruction;

12.2.2 Angiography at 180 days and 12 months post-procedure

Sites shall send the following images (at a minimum):

- AP, Lateral and working projections;

- Working projections selected for FRED deployment (pre-deployment);
- Working angles (post-FRED deployment);
- If available, imaging should include 3D reconstruction;
- The investigator should take proper steps to ensure that follow-ups angiograms are performed using similar views.

13.0 Adverse Events

13.1 Definitions

- **Adverse Event (AE):**

Any unfavorable and unintended sign (including laboratory findings), symptom or disease that occurs to a subject while enrolled in this clinical investigation. Medical conditions that exist at study enrollment are not considered an AE unless condition worsens after use of the study device or antithrombotic medications.

- **Serious Adverse Event (SAE):**

A serious adverse event is any medical experience regardless of its relationship to the study treatment that occurs during subject enrollment in this trial that results in any of the following: (1) inpatient hospitalization or prolongation of a hospitalization; (b) persistent or significant disability/incapacity; (c) death of the study subject, or (d) necessitates an intervention to prevent a permanent impairment of a body function or permanent damage to a body structure.

- **Unanticipated Adverse Device Effect (UADE):**

Any serious adverse effect on health or safety or any life-threatening problem or death caused by or associated with a device, if that effect, problem or death was not previously identified in nature, severity or degree of incidence in the investigational plan or IDE application (including a supplementary plan or application), or any other unanticipated serious problem associated with a device that related to the rights, safety or welfare of subjects.

The common terminology criteria for adverse events (CTCAE) will be utilized for Adverse Event (AE) reporting. The CTCAE v.4.0 incorporates certain elements of the MedDRA terminology and the list is incorporated into the Manual of Operating Procedures.

Table 2 Adverse Event Reporting and Device Malfunction

Classification	Reporting time	Type of report
Unanticipated Adverse Device Effects (UADE)	Within 24 hours of learning of event; no more than 10 working days from learning of event	Adverse Event Reporting Form to be submitted to the sponsor, CRO and IRB according to the IRB policies in place at that institution. ¹
Serious AE (SAE)	Within 24 hours of learning of event; no more than 10 working days from learning of event	Serious Adverse Event Reporting Form to be submitted to the sponsor, CRO and IRB according to the IRB policies in place at that institution. ¹
Non-serious AE	Within 30 working days of event.	Adverse Event Reporting Form in EDC
Device Malfunctioning With or Without Adverse Event	Within 5 working days of learning the event	Investigational Clinical Device Product Complaint and Return Form to be submitted to the sponsor, CRO and IRB according to the IRB policies in place at that institution. In case of death, it should be submitted to the FDA, Sponsor, CRO and IRB according to the IRB policies in place at that institution. ¹

¹ Note: Participating clinical sites have different IRBs that sometimes have varying Adverse Event reporting policies. Some request that all AEs be reported; others only request that only the SAEs and UADEs be reported. Regardless of this direction by site specific IRBs, MicroVention and its associated CROs require sites to report all AEs (including UADE reporting, serious AE, Non serious AE, Device Malfunction with or without AE) in an appropriate timeframe. No limitation of the reporting of adverse events are made by the sponsor (MicroVention), CRO and FDA.

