Additionally, other safety endpoints will also be assessed based on Adverse Events. The number of subjects and the number of adverse events per subjects will be presented for Adverse Events, unanticipated Adverse Events, Serious Adverse Events, and unanticipated Serious Adverse Events. The results will be provided by system organ class and preferred term. Narrative case summaries will be provided for each Serious Adverse Event. Two-sided 95% credible intervals will be presented for each adverse event with ≥5% incidence.

Technical Failures

Technical failure subjects will be presented separately but will be excluded from the ITT and Per Protocol populations if they did not receive the device. They will be included in the Safety population.

A FRED procedure will be categorized as a technical failure if the following occurs:

- Failed FRED Device Deployment Due to Technical Issues with the FRED Device
 - If the FRED Device enters the blood stream and cannot be deployed secondary to technical issues with the device itself (e.g., FRED Device malfunction or failure to access the target site due to the FRED Device), the Subject will be counted as enrolled with intent-to-treat. This will be considered as a secondary endpoint failure. The Subject will be maintained within the study and will not be replaced by another Subject. The Subject will be monitored for any Adverse Event for one (1) week

following the failed deployment due to a technical issue related to the FRED Device. Unless medically necessary to pursue treatment sooner, it is recommended that further attempts to treat the target aneurysm be deferred for a minimum of one (1) week so that any potential procedural Adverse Events may be monitored.

- Failed Device Deployment Due to Issues Related to the Procedure

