13.2 Anticipated Adverse Device Effects

The following potential risks and complications are known to be associated with cerebral angiography, intracranial catheterization, intracranial stent/ flow diverters placement and would not be considered as UADEs:

- Allergic reaction, including but not limited to, imaging contrast dye, nitinol metal, and any other medications used during the procedure;
- Aneurysm rupture;
- Aneurysm growth;
- Bleeding including intracerebral, retroperitoneal or in other locations (Note: reportable events involving bleeding are not limited to those related to the procedure);
- Blindness;
- Cardiac arrhythmias;
- Cranial neuropathy;
- Device fracture, migration or misplacement;
- Device thrombosis;
- Diplopia;
- Dissection or perforation of the parent artery;
- Emboli;
- Failure to deliver the device;
- Failure to deploy the device at the intended target site;
- Headache;
- Hemorrhage;
- Hematoma / Hypoperfusion;
- Infection;
- Injury to normal vessel or tissue;
- Ischemia;
- Mass effect;
- Myocardial Infarction;
- Neurological deficits;
- Occlusion of non-target side branches;
- Pseudoaneurysm formation;
- Renal failure;
- Stenosis of stented segment;
- Seizure;
- Stenosis or thrombosis of the parent artery or a side branch vessel;
- Stroke or TIA (Transient Ischemic Attack);
- Thromboembolic event;

- Total occlusion of treated parent vessel segment;
- Vasospasm;
- Vessel perforation;
- Visual impairment.

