3.4 SECONDARY ENDPOINTS

Secondary endpoints described in the protocol are listed below:

1. Proportion of subjects with clinically acceptable (90-100%) occlusion of the target aneurysm, $\leq 50\%$ stenosis of the parent artery at the target IA at 12 months (+ 60 days, - 30 days), as assessed by angiography, and in whom an unplanned alternative treatment of the target IA had not been performed within 12 months

2. Proportion of subjects in whom an unplanned alternative treatment of the target IA had not been performed within 12 months
3. Proportions of subjects with clinically acceptable aneurysm occlusion (90 %-100 %) of the target aneurysm at 12 months (+ 60 days, -30 days).
4. Incidence of $\geq 50\%$ In-Stent Stenosis (ISS) at the target IA at 12 months as assessed by angiography at an independent corelab
5. Proportion of subjects with complete occlusion of the target aneurysm on 12-month angiography (+ 60 days, -30 days).
6. Incidence of FRED System procedure related Serious Adverse Events
7. Incidence of FRED System device-related Serious Adverse Events;
8. Incidence of unsuccessful delivery of the FRED system implant;
9. Incidence of unsuccessful deployment of the FRED flow-diverter intra-cranial stent
10. Incidence of migration of the FRED system implant at 12 months;
11. Unplanned alternative treatment on the target IA within 12 months, defined as re-treatment of the target aneurysm with an alternative treatment modality including open repair, endovascular placement of an additional stent or treatment of In-stent Stenosis observed at the 180 day or 12 month follow-up time-points or at an unscheduled study follow up visit.
12. Change in clinical and functional outcomes at 180 days and 1 year follow up, as measured by an increase in the modified Rankin Scale compared to baseline;
13. Incidence of major stroke, as measured by NIHSS at 12 months (and ophthalmic examination related to the target aneurysm if determined appropriate).
14. Incidence of minor stroke, as measured by NIHSS at 12 months (and ophthalmic examination related to the target aneurysm if determined appropriate).

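### The SAE definition has no life-threatening criterion, so some index-stay events can be labelled non-serious and left out of the SAE endpoints and narratives

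*Protocol*

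**What the plan says.** Protocol Section 13.1 defines an SAE by outcome, whatever its relation to treatment. The first three criteria are "1) inpatient hospitalization or prolongation of a hospitalization; (b) persistent or significant disability/incapacity; (c) death of the study subject". The fourth is "d) necessitates an intervention to prevent a permanent impairment of a body function or permanent damage to a body structure".

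The UADE definition in the same section is wider on one point. It covers "Any serious adverse effect on health or safety or any life-threatening problem or death caused by or associated with a device", but only "if that effect, problem or death was not previously identified in nature, severity or degree of incidence". Section 13.2 then lists known risks that "would not be considered as UADEs". The list includes allergic reaction, cardiac arrhythmias, hemorrhage, aneurysm rupture, vessel perforation and myocardial infarction.

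Seriousness drives four things in the plan:

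- **Endpoints.** Secondary endpoint 6 is "Incidence of FRED System procedure related Serious Adverse Events", and endpoint 7 is the device-related counterpart (Protocol Section 5.5, SAP Section 3.4).
- **Narratives.** Protocol Section 6.2 states: "Narrative case summaries will be provided for each Serious Adverse Event".
- **Reporting time.** In Table 2, SAEs and UADEs are due within 24 hours of learning of the event, with an outer limit of 10 working days. Non-serious AEs are due "Within 30 working days of event".
- **IRB reporting.** The note to Table 2 says that some IRBs ask only for SAEs and UADEs.

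The SAP tabulates SAEs from CEC assessments (Sections 8 to 8.2) and gives no definition of seriousness of its own.

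**The concern.** Treatment is under general anesthesia (Protocol Section 11.3), and the subject stays in hospital until the discharge assessment. During that stay the hospitalization criterion can be met only if the stay is prolonged. Procedural risk is concentrated in the same period. An event that threatens life but is reversed quickly and leaves nothing behind can therefore miss every SAE criterion. The protocol recognises the life-threatening category, because the UADE definition uses it, but that route is closed to anticipated events and to events not associated with the device.

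What is at stake is how completely endpoints 6 and 7, the SAE tables and the SAE narratives describe the procedure's risk, and whether some IRBs are told of such events at all.

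**Working it through.** The plan gives no figure to reproduce, because this is a question of definitions. The check takes one hypothetical event through the rules: an arrhythmia or allergic reaction during the index stay that is life-threatening when it occurs and resolves fully before the planned discharge.

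1. **Hospitalization or prolongation.** The subject is already an inpatient and the stay is not extended. Not met.
2. **Persistent or significant disability.** Full recovery. Not met.
3. **Death.** Not met.
4. **Intervention to prevent permanent impairment or damage.** Not met if no intervention with that purpose was needed. This step catches many life-threatening events, so only a residual subset passes it.
5. **UADE.** Both event types are on the Section 13.2 list, so they are excluded. An event not associated with the device fails the UADE definition in any case.
6. **Result.** The event is a non-serious AE as written. Neither document contains another seriousness definition that would change this.

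**Effect on reporting time.** Two provisions apply, and they differ.

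- Footnote 3 of the Summary of Events puts device-related AEs on the schedule of 24 hours, at most 10 working days from awareness, with no condition on seriousness.
- Table 2 puts all non-serious AEs on the 30-working-day line and does not reflect the footnote.

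Only an event that is not device-related falls under the 30-working-day line alone. The two limits cannot be compared directly: 10 working days runs from learning of the event and 30 from the event itself.

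**Effect on incidence.** SAP Sections 8.1 and 8.2 report the percentage of subjects with one or more events. The SAP's Study Design summary gives 145 subjects in the Safety cohort, and the power table in SAP Section 7.2 uses 140.

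- Largest change from one event at n = 145: 1/145 = 0.69 percentage points.
- Largest change at n = 140: 1/140 = 0.71 percentage points.
- If the subject already has another qualifying SAE, the change is 0.
- Endpoint 6 or 7 changes only if the event is also adjudicated procedure- or device-related.

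The documents give no basis for estimating how many such events there are.

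**The case against.** The strongest reply is that little is lost. The fourth criterion, or a prolonged stay, will catch most ruptures and perforations, and a life-threatening event after discharge that leads to admission is serious on the first criterion. The sponsor requires all AEs to be reported (note to Table 2). The CEC adjudicates all of them, and the DSMB reviews all site-reported and CEC-adjudicated data (SAP Section 4.1). The primary safety endpoint rests on death and NIHSS-defined stroke. Endpoints 6 and 7 are descriptive, with no hypothesis test (SAP Section 7.6.1). The Manual of Operating Procedures and the CEC manual are not among the documents and may already contain the criterion.

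All of that stands, and it limits the point. It also rules out three stronger readings that a reader might infer:

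- **Such events escape the DSMB.** They do not, because its review is not confined to SAEs.
- **All such events reach the sponsor late.** Footnote 3 already sets the faster schedule for device-related AEs.
- **Each such event lowers the SAE rate by 0.69 points.** That figure is a ceiling, because the percentages count subjects and not events.

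What the reply does not remove is the misclassification. Full reporting does not put a non-serious event into endpoints 6 and 7 or give it an SAE narrative, and in these documents the CEC has no life-threatening criterion to apply. If a manual does contain one, Section 13.1 should still state it, since that is where the protocol defines an SAE.

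**Conclusion.** The omission is real and inconsistent with the UADE definition beside it. A narrow class of life-threatening index-stay events can be labelled non-serious. Those events would be left out of endpoints 6 and 7, the SAE tables and the SAE narratives, and might not reach IRBs that ask only for SAEs and UADEs. The events remain in the AE data, and study success does not depend on them. The effect is probably small: at most 0.69 percentage points of subject-level SAE incidence per event at n = 145, and often nothing.

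This assumes that no document outside the protocol and SAP supplies the missing criterion, and that at least some such events resolve without meeting the fourth one. It is a modest point, worth correcting because safety classification should not depend on whether the patient was already in hospital.

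**What to change.** Add a life-threatening criterion to the SAE definition in Protocol Section 13.1, matching the category already in the UADE text, and carry it into the SAE form and CEC guidance. Have the CEC apply it to the recorded AEs before endpoints 6 and 7 are tabulated, and write narratives for any event reclassified. Reconcile Table 2 with footnote 3 of the Summary of Events, so that the reporting time for non-serious device-related AEs is stated once.

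The text change is short. The real cost is re-review: the SAP describes subjects as already enrolled and treated, so the CEC would have to look again at AEs already collected. The SAE count may rise slightly. Sample size, the primary analyses and the success criteria do not change.
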